10.8. Appendix 8: Protocol Amendment History

The Protocol Amendment Summary of Changes Table for the current amendment is located directly before the Table of Contents (TOC).

Amendment 3 (date): 29 Nov 2022

Overall Rationale for the amendment

Based on feedback received from top pulmonologists, and review of similar studies conducted in India, the total number of at clinic visits is reduced from 4 to 3 and run-in period on existing COPD medication for 2 weeks has been removed. These changes are expected to simplify the study, reduce the patient burden participant drop-out rates without compromising the quality of the study.

Approximately 306 participants will be screened in order to enroll 229 to the study treatment phase (assuming 25% screen failure rate) and achieve 220 evaluable participants at the end of the study (assuming 4% withdrawal from study treatment).

Section # and Name	Description of Change	Brief Rationale
1.1 Synopsis	
Secondary Endpoint: change from baseline and mean change from baseline in trough FEV1 on Day 84 removed
 
Overall Design: Participants will enter run-in on their existing COPD medication for 2 weeks post screening removed.
 
Updated Day 84 visit from physical visit to telephone visit
 
Number of Participants: number of participants screening changed from 336 to 306.
 
Intervention: Groups and Duration: The total duration of participant participation will be approximately 13 weeks.
 
Information on prescription data from India to be used to cap the approximate number of patients enrolled on the most widely prescribed COPD medications is removed
	These changes are expected to simplify the study, reduce the patient burden without compromising the quality of the study.

1.2 Study Design Schema	Updated Schema to reflect the proposed amendments	These changes are expected to simplify the study, reduce the patient burden without compromising the quality of the study.
1.3 Schedule of Activities (SoA)	Updated the following: Day 84 visit from physical to telephonic, activities and related instructions in footnote. Updated Day 85 clinic visit activities. Run-in on their existing COPD medication for 2 weeks post screening removed.	These changes are expected to simplify the study, reduce the patient burden without compromising the quality of the study.
3 Objectives and endpoints/Estimands	Secondary Endpoint: Change from baseline and mean change from baseline in trough FEV1 on Day 84 removed	Since, Day 84 visit is replaced to a telephonic visit for medication reminder and effect of FF/UME/C/VI on lung function is evaluated on Day 85
4.1 Overall Design	Updated Day 84 visit from physical visit to telephone visit Participants will enter run-in on their existing COPD medication for 2 weeks post screening removed. Number of participants screening changed from 336 to 306. Text pertaining to participants enrolled are representative of the population that may be eligible for SITT is removed	These changes are expected to simplify the study, reduce the patient burden without compromising the quality of the study.
5 Study Population,	5.1 Inclusion criteria #7 Patient with history of ≥ 2 moderate exacerbations or one severe (hospitalized) exacerbation in the previous 12 months, and with a score of ≥ 10 on the CAT eligible for the study treatment in the opinion of the investigator and	To ensure right participants are enrolled in the study.

	
documented post salbutamol FEV1/FVC ratio of <0.70
 
#8 clarification Existing COPD maintenance treatment: To be eligible for the study treatment phase, participants must be compliant with their existing COPD maintenance therapy (in the opinion of the investigator) for the preceding two weeks prior to screening.
 
Updated Section 5.2 Exclusion Criteria section to include
 
Documented (medical records) evidence of reversibility.
 
Participants who are non-compliant to their current COPD maintenance therapy for two weeks prior to screening (in the opinion of the investigator) will be excluded
 
Update below exclusion criteria – removed reference to run-in and updated changes
 
Pneumonia and/or moderate or severe COPD exacerbation that has not resolved at least 14 days prior to Screening and at least 30 days following the last dose of oral/systemic corticosteroids (if applicable). In addition, any participant that experiences pneumonia and/or moderate or severe COPD exacerbation within the preceding two weeks prior to screening will be excluded
	
5.3 Treatment Phase Criteria	
1. Compliance with current COPD maintenance therapy
 
 • Participants who are non-compliant to their current COPD maintenance therapy for two weeks 	To ensure right patient is enrolled in the study

	
prior to screening (in the opinion of the investigator) will be excluded
 
2. Pneumonia and/or moderate or severe COPD exacerbation that has not resolved at least 14 days prior to Screening and at least 30 days following the last dose of oral/systemic corticosteroids and/or antibiotics (if applicable). In addition, any participant that experiences pneumonia and/or moderate or severe COPD exacerbation within the preceding two weeks prior to screening will be excluded.
	
5.5 Screen Failures	
Pneumonia and/or moderate or severe COPD exacerbation that has not resolved at least 14 days prior to Screening and at least 30 days following the last dose of oral/systemic corticosteroids and/or antibiotics (if applicable). In addition, any participant that experiences pneumonia and/or moderate or severe COPD exacerbation within the preceding two weeks prior to screening will be excluded and may not be rescreened. and may not be rescreened.
	To ensure right patient/participant is enrolled in the study
6.8 Concomitant Therapy	Removed text pertaining to run-in period.	These changes are expected to simplify the study, reduce the patient burden without compromising the quality of the study.
8.3 Adverse Events (AEs), Serious Adverse Events (SAEs) and Other Safety Reporting	
Updated section to align with local regulatory safety reporting procedures inputs from Named Safety Contact
 
Removed Sentinel events.
	
To align with local reporting procedures
 
Sentinel Event Management process is now retired for studies

9.2 Sample Size Determination	Updated the total number of screened subjects in the study	Considering removal of run-in period, the sample size has been updated

9.3 Analysis sets	Updated text for Screened population and added Enrolled population definition	To align with GSK standard to present the subjects disposition data
9.4.1Efficacy analyses	Removed the change from baseline in trough FEV1 on Day 84 analysis	Since, Day 84 visit is replaced to a telephonic visit and effect of FF/UMEC/VI on lung function is evaluated on Day 85
All Relevant sections	All sections relevant to the key changes were updated	To align with the proposed changes to the protocol around. "run-in period" and Day 84 related schedule or assessments

Amendment 2 30-MAR-2021

Overall Rationale for the Amendment:

Based on feedback and recommendations from the Subject Expert Committee (SEC) in India, the sample size of the study has been increased from 115 to 229 participants, to increase the probability of observing adverse events that make up the well-established safety profile of FF/UMEC/VI. In addition, the increase in sample size improves the precision of the estimate of the lung function endpoint, which is a secondary objective of the study.

Approximately 306 participants will be screened in order to recruit 229 to the study treatment phase (assuming 25% screen failure rate) and achieve 220 evaluable participants at the end of the study (assuming 4% withdrawal from study treatment).

Section # and Name	Description of Change	Brief Rationale
1.3 Schedule of Activities (SoA)	
Removed blood pressure and temperature from footnote f.
 
Removed exacerbation assessment from V1.
	
This was a duplication, blood pressure and temperature are included in the vital signs assessments (footnote g).
 
This was included in error, exacerbation history is collected as V1.

3 Objectives and endpoints/Estimands	
Removed below text change from baseline in trough FEV1 on Day 84 (trough FEV1 on Day 84 is defined as the mean of the FEV1 values obtained prior to dosing on Day 84)
 
mean change from baseline in trough FEV1 on Day 84
	Consistent with changes i.e. day 84 will now be telephone call
9.2 Sample Size Determination	The sample size text and associated probabilities table has been updated.	To reflect the increase in sample size.
10.5.6 Onset and Resolution of COPD Exacerbations	Reference to participant diaries has been removed.	This text was included in error.

Amendment 1: 17 Nov 2020

Overall Rationale for the Amendment:

Following review by and presentation of the protocol to the Subject Expert Committee (SEC) in India, the SEC confirmed that the primary reason for requesting that GSK conduct a study, is to provide safety data that is representative of the COPD population in India. For this reason, the primary objective of the study has been amended. The primary objective of the study is to evaluate the safety profile of FF/UMEC/VI over 12 weeks. Lung function objectives are now included in the secondary objectives and associated endpoints.

Section # and Name	Description of Change	Brief Rationale
1.1 Synopsis 2.1 Study Rational 4.2 Scientific Rationale for Study Design	Text has been updated to reflect that the collection of safety data is the primary reason for conducting the study.	To ensure provision of safety data representative of the COPD population in India in line with local regulations
1.1 Synopsis 3 Objectives and Endpoints/Estimands	The primary and secondary objectives and associated endpoints/estimands have been switched, to make safety the primary objective and efficacy (lung function) the secondary objective of the study.	To ensure provision of safety data representative of the COPD population in India in line with local regulations
9.1 Statistical Hypotheses	The primary and secondary objectives have been updated to reflect that the analysis of safety data is the primary objective and the analysis of lung function data is the secondary objective of the study.	Safety is now the primary objective of the study, and efficacy (lung function) is the secondary objective.
9.2 Sample Size Determination	This section has been updated to reflect that the sample size is now determined based on the calculation of the probability of observing an AE.	Safety is now the primary objective of the study, and so the sample size is determined by a safety endpoint.
9.4 Statistical Analyses	Section 9.4.1 and Section 9.4.2 have been updated to define the statistical analyses as efficacy (Section 9.4.1) and safety (Section 9.4.2) and to reflect that safety is the primary objective of the study.	Safety is now the primary objective of the study, and efficacy (lung function) is the secondary objective.

SAE	Serious adverse event
SAP	Statistical Analysis Plan
SD	Standard deviation
SOC	System organ class
TEAEs	Treatment-emergent adverse events
TLFs	Tables, data listings and figures
WHO	World Health Organization
WHO-DD	WHO Drug Dictionary

1. Overview

1.1 Introduction

The purpose of this Statistical Analysis Plan (SAP) is to provide details of the statistical analyses that have been outlined within the Protocol Amendment No. 4 for 212655 dated 03 May 2023. The scope of this plan includes the final analysis, which will be executed by the Biostatistics department unless otherwise specified. Any post-hoc or unplanned analyses performed but not described in this SAP will be clearly described in the CSR.

2. Trial objectives

The following objectives are those stated in the protocol.

Objectives	Estimands/ Endpoints
Primary	

 To evaluate the safety profile of FF/UMEV/VI over 12 weeks in patients from India 	
The primary Estimand is defined by the following:
 
 Endpoint: incidence of adverse events (AE), serious adverse events (SAE) and adverse events of special interest (AESIs). Summary number and percentage of participants experiencing an AEs, SAEs and number and percentage of participants experiencing AESIs by system organ class and by preferred term. Population of interest: COPD patients in India. Key intercurrent events: discontinuation of treatment Strategy for intercurrent events: a While on Treatment strategy will be used for treatment discontinuation. This estimates the percentage of participants experiencing an AE or SAE while taking treatment. Participants that test positive for COVID-19 will immediately discontinue study treatment. Therefore COVID-19 will be included as the intercurrent event of study treatment discontinuation and will be handled with While on Treatment strategy for the primary estimand. A supplementary estimand will be defined using identical properties as for the primary estimand (summary measure, population of interest and key intercurrent events), however this supplementary estimand will report all AEs regardless of the discontinuation of study treatment.

[figure not shown]
	
• Endpoints:
• Incidence of AEs, SAEs and AESIs• Strategy for intercurrent events:
• Treatment policy strategy will be used for treatment discontinuation. This summary will therefore be inclusive of all on-treatment and post-treatment AEs.
Secondary	

• To evaluate the effect of FF/UMEC/VI on lung function	
The secondary Estimands are defined by the following:
 
• Endpoints:
• change from baseline in trough FEV1 on Day 85 (trough FEV1 on Day 85 is defined as the mean of the FEV1 values obtained 24 hours after morning dosing on Day 84)• change from baseline in trough FEV1 on Day 28 (trough FEV1 on Day 28 is defined as the mean of the FEV1 values obtained prior to dosing on Day 28)• Summary measure:
• mean change from baseline in trough FEV1 on Day 85• mean change from baseline in trough FEV1 on Day 28• Population of interest: COPD patients in India.• Key intercurrent events: discontinuation of treatment• Strategy for intercurrent events: a hypothetical strategy will be used for treatment discontinuation. This estimates the effect under the hypothetical scenario that participants had not discontinued treatment.• Participants that test positive for COVID-19 will immediately discontinue study treatment. Therefore COVID-19 will be included as the intercurrent event of study treatment discontinuation and will be handled with hypothetical strategy for the secondary estimands.

3. Trial design

3.1 Design overview

This is a phase IV, 12-week, single arm, multi-centre study evaluating single inhaler triple therapy (FF/UMECH/VI) once daily via the ELLIPTA inhaler.

Figure 4.1.1 Study Design Schema

*At day 84 (telephonic visit), participant will be instructed by the investigator telephonically to take the morning dose of study treatment/COPD medication, between 8am and 11am.

Approximately 306 participants will be screened to enrolled 229 (assuming 25% screen failure) to the study treatment phase for achieving 220 evaluable participants at the end of the study (assuming 4% withdrawal from study treatment).

At the start of the treatment period, participants will discontinue all existing COPD medications but may continue their study-supplied rescue salbutamol on an as-needed basis (rescue medication) throughout the study.

Clinic Visits will occur at Pre-Screening (Visit 0), Screening (Visit 1), Start of Treatment (Day 1, Visit 2), Day 28 (Visit 3), and Day 85 (Visit 5). Day 84 (Telephonic Visit 4) and Safety follow-up (Visit 6) conducted 1 week after completing the 12-week treatment period will be a telephone contact. Participants will sign an informed consent form (ICF) at a Pre-Screen or Screening Visit and will be assigned a participant identifier. Note: Visit 0 and Screening (Visit 1) may occur on the same day based on discretion of the study participant and discretion of Investigator.

3.2 Schedule of events

Refer to section 1.3 schedule of activities of the protocol.

4. Changes/deviations from the planned analysis

The statistical analysis/methods as described in the protocol were adopted. For secondary endpoint analysis, as mentioned in the protocol, treatment policy shall be used as supplementary estimand for secondary endpoints if >5% of the ITT participants discontinued study treatment. However as per the discussion of study team analysis will be done using treatment policy (as supplementary estimands) even if 5% do not discontinue the study treatment. That is the condition of 5% will not be applicable.

Any deviation from original statistical analysis plan will be described and justified in the SAP or final clinical study report.

5. Analysis populations

The following sets will be used for the statistical analyses:

5.1 Screened population

This population will include all participants for whom a record exists in the study database, including screen failures and any participant who was not screened but experienced an SAE between the date of informed consent and the planned date of the screening visit.

5.2 Enrolled population (ENRL)

This population will include all participants who signed the informed consent form (ICF), and screen passed and who received study intervention or underwent a post-screening procedure.

NOTE: Participants screened but never enrolled into the study (Met eligibility but not needed) are excluded from the Enrolled Analysis set as they did not enter the study.

5.3 Intended-to-Treat population (ITT)

This analysis population will include all participants who received at least one dose of study treatment.

6. General considerations

6.1 Baseline

Baseline is defined as the last non-missing observation made prior to the first administration of study treatment including those from unscheduled visits. If time is not collected, Day 1 assessments are assumed to be taken prior to first dose and used as baseline. Unless otherwise stated, if baseline data is missing no derivation will be performed and baseline will be set to missing.

Participants who prematurely withdrew from study will not be replaced. For ECG, if the latest, non-missing pre-dose values is from triplicate, the subject level baseline is defined as the mean of triplicate baseline assessments.

6.2 Stratification

This is single arm trial; hence, stratification is not required.

6.3 Statistical tests

There will be no formal hypothesis testing for this study. Mixed model repeated measure model (MMRM) will be used for secondary efficacy analysis.

6.4 Common calculations

For quantitative measurements, change from baseline will be calculated as: (Test value at Visit Day X – Baseline value), where the baseline value is defined as the last non-missing observation taken prior to first exposure to study treatment.

6.5 Software

All analyses will be conducted using SAS® Version 9.4 or higher.

7. Statistical considerations

7.1 Multicentre studies

This study will be conducted over multiple centres.

7.2 Missing data

For efficacy data, missing values will be assumed to be missing at random (MAR) & no imputation will be performed.

For adverse event, prior and concomitant medication data, partial date imputations will be performed where at least the year is provided.

8. Output presentations

The templates provided in the separate output templates document describe the format and content for presentation of tables, listings, and figures (TLFs).

For continuous measures, summary statistics will include number of participants (n), mean, standard deviation (SD), median, minimum, and maximum for both the actual and the change from baseline measurements. For categorical measures, summary statistics will include number of participants (n), frequency, and percentages.

All percentages (%) for a specific summary are calculated using the total number of participants included in the relevant analysis population as the denominator, unless otherwise specified.

9. Participant disposition and withdrawal

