7. DISCONTINUATION OF FF/UMEC/VI AND PARTICIPANT DISCONTINUATION/WITHDRAWAL

7.1. Discontinuation of FF/UMEC/VI

Participants have the right to discontinue FF/UMEC/VI before the end of the study. A participant may also be asked to discontinue FF/UMEC/VI at the Investigator's discretion.

Participants that permanently stop FF/UMEC/VI should return to the clinic as soon as possible, in order to complete the Treatment Discontinuation visit. The evaluations and procedures to be completed are outlined in the SoA (Section 1.3)

Participants that discontinue FF/UMEC/VI are encouraged to remain in the study and every effort should be made by the Investigator/staff to keep the participant in the study, to collect important efficacy and safety data.

If possible, participants should return to the clinic to complete all scheduled visits. If this isn't possible, visits should be completed by telephone. Ideally, participants should return to the clinic to complete Visit 5, to collect important spirometry data, however, if this isn't possible, this visit could be completed by telephone. A safety follow-up phone call (Visit 6) should also be conducted 7 days after Visit 5.

Following discontinuation of study intervention, if participants are unwilling to return to the clinic for their scheduled visits, the Investigator/site staff should contact the participant by telephone at the protocol designated visit time intervals to collect the following:

- SAEs
- AEs assessed as related to study participation
- AEs resulting in discontinuation of study intervention or withdrawal from the study
- COPD exacerbations
- Concomitant medication
- A safety follow-up phone call (Visit 6) should also be conducted 7 days after Visit 5.

A participant may be withdrawn from study intervention at any time. A reason for premature discontinuation of study intervention (e.g., AE, lack of efficacy, protocol deviation, Investigator discretion, consent withdrawn etc.) must be captured in the eCRF.

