- **Strategy for intercurrent events:** A hypothetical strategy will be used for treatment discontinuation. This estimates the effect under the hypothetical scenario that participants had not discontinued treatment. Participants that test positive for COVID-19 will immediately discontinue study treatment. Therefore COVID-19 will be included as the intercurrent event of study treatment discontinuation and will be handled with hypothetical strategy for the secondary estimands.
- **Supplementary Estimands:**
Mean change from baseline in trough FEV1 on Day 85.
Mean change from baseline in trough FEV1 on Day 28.
A supplementary estimand will be defined using identical properties (summary measure, population of interest and key intercurrent events), however this supplementary estimand will report the actual values recorded regardless of the discontinuation of study treatment.
- **Strategy For ICE under Supplementary Estimands:** A supplementary estimand will be estimated using treatment policy strategy for the intercurrent event of treatment discontinuation unrelated to the COVID-19 pandemic and using hypothetical strategy for the intercurrent event of treatment discontinuation related to the COVID-19 pandemic.
- **Treatment Policy:** Actual values of the variable regardless of whether the intercurrent event has occurred. This approach requires collection of data after the intercurrent event of interest (e.g. continued collection if a patient discontinues treatment) and corresponds to a full ITT approach. If the patient also withdraws from the study, then this becomes a missing data problem.

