18.1.2 Secondary estimand analyses

Population: Table: ITT
Listing: ITT

Statistics: The mean change in FEV1 values from baseline to Day 28 and Day 85 will be summarized using descriptive statistics (mean, median, SD, minimum, maximum, and number with missing values).

Only scheduled spirometry observations will be used for the analysis and unscheduled spirometry observations will be presented in data listing.

The MMRM model will be used for analysis of the change in FEV1 values from baseline to Day 28 and Day 85. Least-square means, standard error, 95% CI derived from the analysis model will be displayed by day for two models within the MMRM output. The first model will include change from baseline in FEV1 values as response variable, FEV1 values at baseline and day as covariates and an interaction between FEV1 values at baseline and day. Day will be specified as the repeated effect, and with SUBJECT option to account for the repeated measures within subjects. OM will be used in lsmeans statement. An unstructured covariance structure will be used to model the within-participant variability. If this analysis fails to converge, the following covariance structures will be tested in order:

1. Toeplitz with heterogeneity
2. Autoregressive with heterogeneity, by day
3. Compound symmetry with heterogeneous variances, by day
4. Toeplitz
5. Autoregressive
6. Compound symmetry without heterogeneous variances, by day

The first covariance structure that converges will be used. The Kenward-Roger approximation will be used to estimate denominator degrees of freedom. Significance tests will be based on least-squares mean using Type III sum of squares.

The second model will use absolute FEV1 values as response variable, whilst all other components remain the same as described above.

Through FEV1 data collected up to the time of treatment discontinuation will be used in the analysis. This estimates effect under the hypothetical scenario that participants do not discontinue treatment. Through FEV1 collected after treatment discontinuation will be set to missing. Missing data will be assumed to be missing at random (MAR).

A supplementary estimand will be estimated using treatment policy strategy for the intercurrent event of treatment discontinuation unrelated to the COVID-19 pandemic and using hypothetical strategy for the intercurrent event of treatment discontinuation related to the COVID-19 pandemic.

19. Other assessments

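### The supplementary treatment-policy FEV1 analysis keeps the MAR, no-imputation rule, so it drifts toward the hypothetical estimate when stoppers have no later spirometry

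*SAP*

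**What the plan says.** The main FEV1 estimand (Protocol 9.3.1, SAP 18.1) is hypothetical. Values after treatment discontinuation are set to missing and the MMRM is fitted under MAR.

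The supplementary estimand asks a different question. SAP 18.1.2: "A supplementary estimand will be estimated using treatment policy strategy for the intercurrent event of treatment discontinuation unrelated to the COVID-19 pandemic". COVID-related stops stay hypothetical. SAP section 4 drops the protocol's 5% trigger, so this analysis is always run.

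For missing efficacy values, SAP 7.2 gives one rule: "For efficacy data, missing values will be assumed to be missing at random (MAR) & no imputation will be performed". SAP 18.1 recognises the difficulty for participants who leave the study, "If the patient also withdraws from the study, then this becomes a missing data problem", but no method follows. SAP 18.1.2 gives one set of model terms: "The first model will include change from baseline in FEV1 values as response variable, FEV1 values at baseline and day as covariates", plus the baseline-by-day interaction. The second model changes only the response variable. Neither has a term for treatment status.

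On data collection, Protocol 7.1 asks sites to keep stoppers in the study and prefers Visit 5 in clinic so that spirometry is obtained. It then allows a fallback: "if this isn't possible, this visit could be completed by telephone". Protocol Appendix 4 says that spirometry cannot be done at home.

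**The concern.** A treatment-policy mean should reflect what happens to stoppers after they stop. Under MAR with these model terms, a stopper without a later FEV1 is represented by people with similar baseline (and Day 28) values, nearly all of whom are still on FF/UMEC/VI. That is the target of the hypothetical estimand. Stoppers with no post-baseline FEV1 at all drop out of the likelihood, with the same practical effect.

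Such gaps are foreseeable: Visit 5 by telephone, study withdrawal and loss to follow-up. The supplementary result would then sit close to the main one because of how missing values are treated, and a reader could take the agreement as reassurance. If FEV1 is lower off treatment than on it, the supplementary estimate is too high for the estimand it is labelled with.

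**Working it through.** **Inputs from the documents (Protocol 9.2).** 220 evaluable participants, 229 enrolled, 4% withdrawal from treatment, residual SD 240 mL, precision 32 mL (half-width of the 95% CI at Day 85).

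**Assumed inputs (not in the documents).** Mean loss in FEV1 after stopping, 50 to 150 mL; a 10% stopping rate as a stress case; the share of stoppers with later spirometry, 0 to 100%.

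**Step 1: reproduce the plan's figures.**
- Half-width = 1.96 × 240 / √220 = 31.7 mL (31.9 mL with t on 219 df). This matches 32 mL.
- 220 / 0.96 = 229.2, against 229 stated. Expected stoppers: 229 − 220 = 9.

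**Step 2: size of the bias.**
Bias ≈ (share of non-COVID stoppers without later FEV1) × (on-treatment minus off-treatment mean change).

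With no stopper retrieved, and all stops taken as non-COVID:

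| Stopping | Loss 50 mL | Loss 100 mL | Loss 150 mL |
|---|---|---|---|
| 4% | 0.04 × 50 = 2 mL | 4 mL | 6 mL |
| 10% | 0.10 × 50 = 5 mL | 10 mL | 15 mL |

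**Step 3: check by simulation.** 229 participants; Day 28 and Day 85; unstructured covariance with a baseline-by-day effect, fitted by maximum likelihood; SD 240 mL. Further assumptions: true on-treatment change 100 mL, visit correlation 0.6, half of the stoppers stopping before Day 28, loss 100 mL. There were 300 replicates per row. The hypothetical fit sets all post-stop values to missing. The supplementary fit adds only the retrieved off-treatment Day 85 values. Figures are Day 85 means in mL.

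| Stopping | Stoppers retrieved | Hypothetical | Supplementary (MAR) | True treatment-policy mean | Bias |
|---|---|---|---|---|---|
| 4% | 0% | 98.6 | 98.6 | 94.5 | 4.0 |
| 4% | 25% | 100.5 | 99.5 | 96.5 | 3.0 |
| 4% | 50% | 99.5 | 97.4 | 95.6 | 1.8 |
| 4% | 100% | 100.8 | 96.6 | 96.6 | 0.0 |
| 10% | 0% | 101.3 | 101.3 | 91.4 | 9.9 |
| 10% | 25% | 101.4 | 98.7 | 91.6 | 7.1 |
| 10% | 50% | 99.5 | 94.4 | 89.9 | 4.5 |
| 10% | 100% | 100.9 | 90.6 | 90.6 | 0.0 |

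Compare within rows; the level varies between rows by simulation error, and bias is rounded separately. With none retrieved the two estimates coincide and the bias agrees with Step 2. At 25% retrieval about 25 to 30% of the gap is recovered, at 50% about half, and at 100% all of it.

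**The case against.** The strongest reply is that the consequence is slight. At the planned 4%, some nine people, even the worst case is 6 mL against a half-width of 32 mL. FEV1 is secondary, nothing is formally tested, and the primary objective is safety. All of that stands.

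Four stronger readings are tempting, and the documents do not support them.

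- *The supplementary analysis always repeats the main one.* That needs every non-COVID stopper to lack later spirometry. Protocol 7.1 asks for the opposite, and retrieved values are used in the analysis.
- *The gap arises because the Schedule of Activities has no spirometry at the treatment-discontinuation visit.* The endpoints are Day 28 and Day 85 values, and SAP 18.1.2 uses scheduled spirometry only. A reading at an early discontinuation visit would supply neither. Spirometry is already scheduled at Visits 3 and 5.
- *A COVID-19 wave would enlarge the bias through extra stopping.* Protocol 9.2 foresees more discontinuation in that case, but pandemic-related stops are hypothetical in both analyses by design.
- *This is a failed sensitivity analysis of MAR.* The SAP presents it as a supplementary estimand. The criticism is that the method does not fully target that estimand, not that a promised MAR check is broken.

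It is also fair to say that no single imputation model is clearly right. The documents do not say what stoppers take afterwards. They may resume earlier maintenance therapy, take something else, or take FF/UMEC/VI commercially (Protocol 6.6). Any anchor is untestable, so the fix uses a range.

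What remains is that the SAP states a rule which, for non-COVID stoppers without later FEV1, estimates something other than its own estimand.

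**Conclusion.** The point holds as an inexpensive improvement. Applying MAR without imputation to the treatment-policy analysis, with no on/off-treatment term, pulls that estimate toward the hypothetical one to the extent that non-COVID stoppers lack Day 28 or Day 85 spirometry. The two are equal only if none is retrieved.

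In that extreme the bias is 2 to 6 mL at 4% stopping (6/32, or about 19% of the half-width, at most) and 5 to 15 mL at 10%. The direction is upward if off-treatment FEV1 is lower than on-treatment FEV1. These sizes rest on an off-treatment loss of 50 to 150 mL, and the 10% rate is a stress case that the protocol does not plan for.

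The primary safety objective and the main hypothetical FEV1 analysis are unaffected. A reader might infer that the trial's lung-function conclusion is in doubt; nothing here supports that. The issue is how much weight agreement between the two FEV1 analyses can bear.

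**What to change.** In SAP 7.2 and 18.1.2:

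1. Limit MAR without imputation to the hypothetical analysis and, within the supplementary analysis, to COVID-related stops.
2. For the supplementary analysis, keep every observed off-treatment value. Multiply impute missing post-stop FEV1 for non-COVID stoppers from a distribution centred on the participant's own baseline, conditioning on any observed Day 28 value, and combine with Rubin's rules. Baseline is a reasonable anchor because it is measured while participants are on existing maintenance therapy.
3. Repeat over a short pre-specified delta range, for example −50, 0 and +50 mL around baseline, because off-treatment FEV1 is unknown.
4. Show the MAR fit alongside.
5. Report how many Day 28 and Day 85 values are on treatment, observed off treatment, and missing or imputed. SAP 9.1 and 18.1.2 already give discontinuation, withdrawal and missing-value counts; the split by treatment status is new.

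For scale, take an on-treatment change of 100 mL (assumed), 4% stopping and none retrieved. The imputed supplementary mean would be 100 − 0.04 × 100 = 96 mL at delta 0, 94 mL at −50 and 98 mL at +50, against 100 mL under MAR.

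The cost is SAP wording, one imputation program and one extra table, with no new data. The downsides are an untestable anchor, which the delta range makes visible, and probably a slightly less favourable supplementary estimate.
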